6.12.4.2. Systemic Hypersensitivity Reaction

The number and proportion of patients experiencing treatment-emergent potential systemic hypersensitivity reactions will be summarized and compared by treatment group using Fisher's exact test. The following MedDRA SMQ will be used to identify potential systemic hypersensitivity reactions from all TEAEs:

- Anaphylactic reaction (SMQ). Besides using the narrow and broad terms designated within the SMQ, the following search algorithm will also be implemented as another approach to determine if a patient had an anaphylactic reaction: if a patient (had at least 1 event in Category A) or (had at least 1 event that is in category B and also had at least 1 event that is in category C) or (had at least 1 event that is in category D and [also had at least 1 event in category B or at least 1 event in category C])
- Angioedema (SMQ)
- Hypersensitivity (SMQ)

Specifically, need to perform the following: (1) any narrow or algorithmic term from any 1 of the 3 SMQs indicated above (that is, combined search across narrow and algorithmic portions of all 3 SMQs); (2) any narrow scope term within each SMQ, separately (that is, narrow SMQ search); (3) any term within each SMQ, separately (that is, broad SMQ search); (4) narrow scope term search within each SMQ, report the PT nested within each SMQ.

A similar summary will be provided for the TEAE related to study drug judged by investigator.

Note that an individual patient may contribute multiple events. Also, a single event may satisfy multiple SMQs, in which case the event contributes to every applicable SMQ.

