3.3. Benefit/Risk Assessment

More detailed information about the known and expected benefits and risks of insulin lispro may be found in the country-specific product labeling (for example, Patient Information Leaflet, Package Insert, or Summary of Product Characteristics).

Across all doses in the Eli Lilly and Company (Lilly) clinical studies that have evaluated treprostinil as a local vasodilator with or without insulin lispro, there was no clinically significant increase in those adverse events (AEs) associated with systemic absorption of treprostinil, as described in the Remodulin package insert (2014) (that is, headache, diarrhea, nausea, jaw pain, vasodilatation, rash, edema, anorexia, vomiting, asthenia, abdominal pain, and hypotension). The exposures of treprostinil in LY900014 for participants in upcoming and future clinical trials are expected to be much lower than those observed in the dose ranges previously explored with SC bolus administration of treprostinil and are expected to be substantially lower than those observed in the treatment of pulmonary artery hypertension (PAH).

More information about the known and expected benefits, risks, serious AEs (SAEs) and reasonably anticipated AEs of LY900014 can be found in the IB.

4. Objectives and Endpoints

Table ITRN.1 shows the objectives and endpoints of the study.

Table ITRN.1. Objectives and Endpoints

Objectives	Endpoints
Primary Objective	
1. To test the hypothesis that LY900014 is noninferior to insulin lispro on glycemic control (NIM=0.4% for HbA1c) in patients with T2D, when administered as prandial insulin (0 to 2 minutes prior to the meal), in combination with basal insulin glargine or insulin degludec for 26 weeks	1. Difference between LY900014 and insulin lispro in change from baseline to Week 26 in HbA1c
Multiplicity Adjusted Objectives	
2. To test the hypothesis that LY900014 is superior to insulin lispro in controlling 1-hour PPG excursions, when administered as prandial insulin	2. Difference between LY900014 and insulin lispro in the 1-hour PPG excursion (serum glucose measured 1 hour after the start of the meal minus fasting serum glucose) from an MMTT at Week 26

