The definitions of baseline and post-baseline for the efficacy and safety analyses depend on which analysis period is being used. The following analysis periods will be used:

- Lead-in Period – Visits 2 to 8
- 26-Week Treatment Period – from randomization to Week 26 prior to discontinuation of IP and from randomization to Week 26 (including all data regardless of IP use)
- 26-Week Treatment Period and Safety Follow-Up Visit – from randomization to Visit 801 (including all data regardless of IP use)

The data on IP is defined based on the following rules:

- For data only measured at an office visit
 - MMTT postbaseline data will be classified as on IP if the MMTT performance date is prior to or on the last IP dose date
 - Other postbaseline data (for example, vital signs, safety laboratory tests, and questionnaires) will be considered as on IP if the measurement was performed at or prior to the cutoff date defined as 14 days after the last IP dose date
- For data collected as running records with an exact date stamp such as adverse events (AEs) and diary entries where the dates of the measures were not tied with the date of an office visit, postbaseline data with dates \leq (last study drug dose date +1) will be considered as data on IP.

Table 6.2 describes the rules for determining the patient population, baseline and postbaseline observations for the different analysis periods.

For continuous measures, summary statistics will include sample size, mean, SD, median, minimum, and maximum for both the actual and the change from baseline measurements. Least-squares (LS) means and standard errors derived from the analysis models will also be displayed. Treatment comparisons will be displayed showing the treatment difference LS means and the 95% CIs for the treatment differences, along with the p-values for the treatment comparisons.

For categorical measures, summary statistics will include sample size, frequency, and percentages. Fisher's exact test or Pearson's chi-square test will be used for treatment comparisons.

For laboratory values, both conventional (CN) and Systeme International (SI) units will be presented. Therefore, both % and mmol/mol will be presented for HbA1c and both mg/dL and mmol/L will be presented for glucose measurements.

All baseline measures will be analyzed using an analysis of variance (ANOVA) model that has treatment as the model term.

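### The anaphylaxis algorithm in SAP 6.12.4.2 sets no time limit between paired events, so unrelated events months apart can enter the combined count of potential hypersensitivity reactions

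*SAP*

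**What the plan says.** SAP 6.12.4.2 names three standardised MedDRA queries (SMQs), for anaphylactic reaction, angioedema and hypersensitivity, which "will be used to identify potential systemic hypersensitivity reactions from all TEAEs". For the anaphylaxis query it adds an algorithm, described as "another approach to determine if a patient had an anaphylactic reaction". Besides a single category A event, there are two paired routes. In one, the patient "had at least 1 event that is in category B and also had at least 1 event that is in category C". In the other, any category D event is joined by any event from B or C.

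Four outputs follow. Algorithmic hits are named only in the first, a "combined search across narrow and algorithmic portions of all 3 SMQs". The others use narrow or broad terms within each query separately. The section also says: "A similar summary will be provided for the TEAE related to study drug judged by investigator". Treatment groups are compared by Fisher's exact test.

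SAP 6.12.2 and Table 6.5 set the data scope for notable events: all treatment-emergent events from Week 0 to Visit 801, regardless of study insulin use. Neither document adds a time window, a same-episode condition or a severity threshold to the paired routes, and neither lists what categories A to D contain.

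**The concern.** Anaphylaxis is an acute episode. A rule meant to decide whether a patient had one should ask whether the component signs occurred together. This rule asks only whether each type occurred at some time in about 30 weeks. A category B event in Week 2 and a category C event in Week 20 satisfy it. One event of the pair may even fall after study insulin has stopped.

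Elsewhere the SAP does attend to timing. Section 6.12.4.1 merges hypoglycemia records no more than 30 minutes apart. Section 6.12.4.4.3 has reviewers assess how close in time transaminase and bilirubin elevations are. No counterpart is stated for the anaphylaxis pairs.

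What is at stake is the clarity of one safety comparison. Chance pairs add patients to search (1) who had no acute reaction. Because algorithmic hits have no line of their own there, a reader of the table could not take them out.

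**Working it through.** The plan states no figure for this rule, so there is none to reproduce. The check shows what the wording permits and gives an order of magnitude.

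**Inputs from the documents**
- Patients per arm: 670 randomized 1:1 (Protocol 10.1), so 670 / 2 = 335.
- Window: 26 weeks of treatment plus 4 weeks of safety follow-up (Protocol 5.1), so 30 weeks = 210 days.
- Test: Fisher's exact (SAP 6.12.4.2), two-sided 0.05 (SAP 6.1).

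**Assumptions not in the documents**
- Proportions b, c and d of patients with at least one event in categories B, C and D over the window: 2/2/1%, 5/5/2% or 10/10/5%.
- Categories independent of each other, one event per category, onset uniform over 210 days, no true anaphylaxis.

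**Step 1: how far apart chance pairs fall.** Over a 210-day grid, the probability that two unrelated onsets are within one day of each other is (210 + 2 × 209) / 210² = 628 / 44,100 = 1.42%. They are more than 28 days apart in 75% of pairs and more than 90 days apart in 32%.

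**Step 2: chance flags with no time condition.** The rule is (B and C) or (D and (B or C)), so

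P(flag) = bc + d(b + c − 2bc).

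| b / c / d | P(flag) | Flags per arm (× 335) | Flags in trial (× 670) |
|---|---|---|---|
| 2 / 2 / 1% | 0.000792 | 0.27 | 0.53 |
| 5 / 5 / 2% | 0.0044 | 1.5 | 2.9 |
| 10 / 10 / 5% | 0.0190 | 6.4 | 12.7 |

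Middle row: 0.0025 + 0.02 × (0.10 − 0.005) = 0.0025 + 0.0019 = 0.0044.

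Other plausible mixes stay in this range: 5/3/1%, 10/5/2% and 15/8/3% give 0.76, 2.6 and 6.1 per arm.

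**Step 3: chance flags if onsets must be within one day.** Multiplying by 1.42% leaves about 0.01, 0.04 and 0.18 in the whole trial for the three rows, a reduction of about 98.6%. This treats each flag as a single pair. That is a slight approximation, since a few patients would have events in all three categories.

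**Step 4: effect on the comparison if component rates are equal in both arms.** The probability of Fisher p < 0.05 from chance flags alone is below 0.0001, 0.002 and 0.024 for the three rows. False-positive error is not inflated.

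**Step 5: dilution.** Suppose 6 true cases in one arm and 0 in the other, out of 335 each: Fisher p = 0.031. Add 3 chance flags to each arm (9 vs 3) and p = 0.14. Add 6 to each (12 vs 6) and p = 0.23. The 6 vs 0 split is hypothetical and only shows the direction: balanced noise makes a real difference harder to see.

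**The case against.** The strongest reply is that this is a deliberately sensitive screen. The output is labelled as potential reactions, and the algorithm is one approach beside narrow and broad searches. Narrow-term results are shown separately, and a further summary is limited to events the investigator judged related. Serious events are listed and have narratives (SAP 6.12.2, 6.12.8). An excess visible only through the algorithm would stand out against these. This softens the problem, but it does not correct search (1). As written, the drug-related summary carries no time condition either.

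Second, the incidences are assumed, and the calculation counts gross flags. A flagged patient who already has a narrow term in any of the three queries adds nobody to search (1), so the net effect is at most the gross figure. Both points stand.

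Third, no document favours a one-day interval over another. That also stands: the need is for some prespecified close interval, and one day is an example.

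A reader might go further and infer that false hits would gather in the LY900014 arm. Protocol 3.3 lists effects of systemic treprostinil, an excipient in LY900014, including "vasodilatation, rash, edema, anorexia, vomiting, asthenia, abdominal pain, and hypotension". The documents do not support that inference. The same sentence reports no clinically significant increase in those events across the sponsor's studies, and the section expects much lower exposure here. Placing rash, edema or hypotension in category B, C or D would need the query definitions, which neither document gives. The rule is also the same in both blinded arms.

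**Conclusion.** The gap is real and limited. As written, the algorithm can pair events up to about 30 weeks apart and count the patient as an anaphylaxis hit within search (1). Chance flags could number roughly 0.3 to 6 per arm, under independence, uniform onset and incidences that the documents do not supply, so the actual number is unknown. The likely harm is noise that dilutes or blurs a true difference. False-positive error is not inflated when component rates are equal.

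Two further readings should be resisted. The paired events cannot be called minor: the rule sets no severity threshold, but the category contents are not in the documents. Nor would the plan report excess anaphylaxis as such, because search (1) is a merged count of potential reactions with no separate anaphylaxis line.

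The primary and multiplicity-adjusted analyses are unaffected. The change is worth making because it is cheap and makes the count match the acute event it is meant to find.

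**What to change.** In SAP 6.12.4.2:

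- State that a B, C or D pairing meets the algorithm in search (1) only if the onset dates lie within a prespecified close interval, for example the same or adjacent calendar day.
- Report algorithmic hits on their own line as well as in the combined count.
- Keep the any-time hits as a listing for medical review.
- Apply the same condition to the summary of drug-related events.

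The cost is a few lines of SAP text and one date condition in the program. No new data are needed, since SAP 6.1 treats adverse events as "data collected as running records with an exact date stamp such as adverse events (AEs" and diary entries. The downside is that a true episode with a misrecorded onset date would appear only in the listing.

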6.12.4.3. Injection Site Reaction

The injection site reactions will be searched by MedDRA PTs from all TEAEs. The number and percentage of patients experiencing treatment-emergent injection site reaction will be summarized and compared by treatment group using Fisher's exact test.

For injection site reactions identified by MedDRA PTs, the presence and severity of erythema, induration, pain, pruritus and edema (collected on the eCRF) will be summarized for each treatment. There will be no statistical comparison between treatments.

6.12.4.4. Hepatobiliary Events

6.12.4.4.1. Treatment-Emergent Potential Hepatic Disorder

The percentages of patients with treatment-emergent drug-related hepatic disorder events will be summarized and compared by treatment group using MedDRA PT nested within each SMQ ordered by decreasing frequency. The following SMQs based on MedDRA will be used to identify potential hepatic disorders:

- broad and narrow terms in the Liver related investigations, signs and symptoms SMQ (20000008)
- broad and narrow terms in the Cholestasis and jaundice of hepatic origin SMQ (20000009)
- broad and narrow terms in the Hepatitis non-infections SMQ (20000010)
- broad and narrow terms in the Hepatic failure, fibrosis and cirrhosis and other liver damage SMQ (20000013)
- narrow terms in the Liver-related coagulation and bleeding disturbances SMQ (20000015)

The percentage of patients with any 1 of the terms will be summarized in addition to the percentages for each MedDRA PT. The percentages of patients with potentially drug-related hepatic disorders that led to permanent study treatment discontinuation will be summarized similarly.

6.12.4.4.2. Liver Enzyme Lab Values

The liver enzyme measures (alanine aminotransferase [ALT], aspartate aminotransferase [AST], alkaline phosphatase [ALP], direct bilirubin, total bilirubin) will be summarized by treatment group. Post-baseline value and the change from baseline (last nonmissing value before randomization) to post-baseline value at Week 26 visit (planned test) will be summarized for patients who have both a baseline and at least 1 postbaseline result, and compared between treatment groups by using ANCOVA model with the term of treatment and baseline value of the response variable. All analyses will be provided in both SI and CN units.

The last nonmissing observation at or prior to Week 26 (including early discontinuation visits) will also be analyzed by an ANCOVA model with the term of treatment, baseline value of response variable.

6.12.4.4.3. Treatment-Emergent Elevation of Liver Enzyme Lab Values

The percentages of patients with the following elevations in hepatic laboratory tests at any time during the treatment period (0 to 26 weeks) will be summarized between treatment groups:

- The percentages of patients with post-baseline ALT measurement ≥ 3 times (3X), 5 times (5X), and 10 times (10X) the Covance upper limit of normal (ULN) will be summarized for all patients with a post-baseline value by the following baseline categories: $\leq 1X$, $>1X$ to $<3X$, $\geq 3X$, missing.
- The percentages of patients with post-baseline AST measurement greater than or equal to 3 3X, 5X, and 10X the Covance ULN will be summarized for all patients with a post-baseline value by the following baseline categories: $\leq 1X$, $>1X$ to $<3X$, $\geq 3X$, missing.
- The percentages of patients with post-baseline total bilirubin measurement ≥ 2 times (2X) the Covance ULN will be summarized for all patients with a post-baseline value by the following baseline categories: $\leq 1X$, $>1X$ to $<2X$, $\geq 2X$, missing.

Baseline will be the maximum observation in the baseline period including the lead-in period. The maximum value will be the maximum value from the treatment period. Planned and unplanned tests will be included.

Graphical profiles of ALT, AST, total bilirubin, and ALP will be provided for patients with an ALT or AST $\geq 3X$ ULN or total bilirubin $\geq 2X$ ULN during the treatment period. A listing for these patients will also be provided, including the actual measurement of ALT, AST, ALP, and total bilirubin, the corresponding reference high limits, demographics, disposition, drug exposure and AEs. The review for these patients includes an assessment of the proximity of any ALT or AST elevation to any total bilirubin elevation, ALP levels, other potential causes, and the temporal association with events such as nausea, vomiting, anorexia, abdominal pain, or fatigue.

All patient data, regardless of whether on IP, will be used for the above analyses related to hepatobiliary events.

6.12.5. Clinical Laboratory Evaluation

The data from safety laboratory measures will be summarized at Week 26 where the lab test is planned to be collected. Postbaseline and change from baseline to postbaseline for laboratory tests will be summarized for patients who have both baseline and at least 1 post-baseline result and compared between treatment groups by using ANCOVA model with the term of treatment and baseline value of the response variable. Analyses will be provided in both SI and CN units.

The last nonmissing observation at or prior to Week 26 (planned tests including early termination) will also be analyzed by an ANCOVA model with the term of treatment, baseline value of the response variable.

The percentages of patients with treatment-emergent abnormal, high, or low laboratory results at any time during the treatment period (0 to 26 weeks) will be summarized for patients who have both baseline and at least 1 post-baseline result and compared between treatment groups using

Fisher's exact tests. A treatment-emergent abnormal result is defined as a change from normal at all baseline visits to abnormal at any time during the treatment period. A treatment-emergent high result is defined as a change from a value less than or equal to the high limit at all baseline visits to a value greater than the high limit at any time during the treatment period. A treatment-emergent low result is defined as a change from a value greater than or equal to the low limit at all baseline visits to a value less than the low limit at any time during the treatment period. Planned and unplanned measurements will be included. Covance reference ranges will generally be used to define the low and high limits. Only patients who have normal baseline values for the analysis being performed will be included in the analysis for treatment-emergence.

Liver enzymes measures will not be included in the above analyses as different analyses will be used as described in Section 6.12.4.4.2 and Section 6.12.4.4.3.

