8.1. Discontinuation from Study Treatment

In the event that the patient is discontinued from the study treatment, the investigator should encourage the patient to remain in the study for continued safety monitoring.

Lilly recognizes the importance of complete data collection. This study includes elements to minimize missing data. Randomized patients who are discontinued from IP before study completion are encouraged to remain in the study for continued monitoring. For patients who remain in the study after early discontinuation of IP, both efficacy (including HbA1c) and safety data will be collected at scheduled visits. The difference between stopping IP and discontinuing the study will be explained to patients as part of the informed consent, and patients will be encouraged to continue in the study even if they stop study drug. In addition, study site investigators will be trained on the importance of complete data collection, with additional re-education of sites and patients as necessary.

8.1.1. *Permanent Discontinuation from Study Treatment*

Patients will be discontinued from the IP in the following circumstances:

- The investigator may decide that the patient should stop IP. If this decision is made because of an AE, SAE, or a clinically significant laboratory value, the study drug is discontinued for that patient and appropriate measures are to be taken. Lilly or its designee is to be alerted.
- The patient may decide to stop IP.
- If the patient becomes pregnant.
- If an investigator, study site personnel performing assessments, or patient is unblinded, the patient must discontinue IP.
- If the patient, for any reason, requires treatment with another therapeutic regimen or therapeutic agent that has been demonstrated to be effective for treatment of the study indication. Discontinuation from IP should occur prior to introduction of the new agent.
- Use of prohibited concomitant medication, see [Table ITRN.8](#).
- If the patient has not taken IP for more than 14 consecutive days.

Discontinuation of the IP for abnormal liver tests **should be considered** by the investigator when a patient meets one of the following conditions after consultation with the Lilly designated medical monitor:

- ALT or AST >8X ULN.
- ALT or AST >5X ULN for more than 2 weeks.
- ALT or AST >3X ULN and TBL >2X ULN or prothrombin time >1.5X ULN.

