- ALT or AST >3X ULN with the appearance of fatigue, nausea, vomiting, right upper-quadrant pain or tenderness, fever, rash, and/or eosinophilia (>5%).
- alkaline phosphatase (ALP) >3X ULN.
- ALP >2.5X ULN and TBL >2X ULN.
- ALP >2.5X ULN with the appearance of fatigue, nausea, vomiting, right upper-quadrant pain or tenderness, fever, rash, and/or eosinophilia (>5%).

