9.4.6. Safety Monitoring

Lilly will periodically review evolving aggregate safety data within the study by appropriate methods.

If a study patient experiences elevated ALT ≥ 3 X ULN, ALP ≥ 2 X ULN, or elevated TBL ≥ 2 X ULN, clinical and laboratory monitoring should be initiated by the investigator. Details for hepatic monitoring depend upon the severity and persistence of observed laboratory test abnormalities. To ensure patient safety and comply with regulatory guidance, the investigator is to consult with the Lilly CRP regarding collection of specific recommended clinical information and follow-up laboratory tests. See [Appendix 4](#).

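### SAP 6.12.5 drops ALP and direct bilirubin from the treatment-emergent laboratory tables in favour of liver sections that contain no elevation analysis for either

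*SAP*

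**What the plan says.** SAP 6.12.5 (Clinical Laboratory Evaluation) plans, for safety laboratory tests generally, ANCOVA on values and changes, and Fisher's exact tests on the percentages of patients with treatment-emergent abnormal, high or low results at any time in Weeks 0 to 26. The percentages count unplanned as well as planned tests. The section ends: "Liver enzymes measures will not be included in the above analyses as different analyses will be used", and it points to 6.12.4.4.2 and 6.12.4.4.3 for those analyses.

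SAP 6.12.4.4.2 says which analytes these are: "The liver enzyme measures (alanine aminotransferase [ALT], aspartate aminotransferase [AST], alkaline phosphatase [ALP], direct bilirubin, total bilirubin) will be summarized by treatment group". Its analyses are continuous only: the Week 26 planned value and the last non-missing value, each by ANCOVA.

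SAP 6.12.4.4.3 gives elevation percentages by baseline category for ALT and AST (at or above 3X, 5X and 10X ULN) and for total bilirubin (at or above 2X ULN). ALP appears there only as a displayed variable: "Graphical profiles of ALT, AST, total bilirubin, and ALP will be provided for patients with an ALT or AST" at or above 3X ULN, or total bilirubin at or above 2X ULN. The listing has the same trigger. Direct bilirubin is not mentioned.

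The protocol treats ALP as a signal in its own right. Under 9.4.6, ALP at or above 2X ULN is one of the findings for which "clinical and laboratory monitoring should be initiated by the investigator". Section 8.1.1 lists "alkaline phosphatase (ALP) >3X ULN" among the conditions for considering discontinuation of investigational product (IP), with two further criteria at ALP above 2.5X ULN: one combined with total bilirubin above 2X ULN, the other with symptoms or eosinophilia.

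**The concern.** An exclusion justified by a replacement analysis is sound only if the replacement exists for everything excluded. Here it exists for three analytes of five. A programmer following the SAP literally would drop ALP and direct bilirubin from the high/low tables and find no other categorical table to put them in.

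What is at stake is the visibility of a cholestatic pattern: ALP raised while ALT and AST stay below 3X ULN and total bilirubin below 2X ULN. An imbalance between arms in such cases would not be counted from the laboratory data, although the protocol asks investigators to act on ALP values of this size.

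**Working it through.** The documents state no figure to reproduce, so the check is one of coverage.

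**Step 1. Each liver measure against each planned laboratory analysis.**

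| Measure (SAP 6.12.4.4.2) | Continuous (6.12.4.4.2) | Treatment-emergent high/low (6.12.5) | Elevation table (6.12.4.4.3) | Triggers profile and listing (6.12.4.4.3) |
|---|---|---|---|---|
| ALT | yes | excluded | yes | yes |
| AST | yes | excluded | yes | yes |
| Total bilirubin | yes | excluded | yes | yes |
| ALP | yes | excluded | no | no (displayed only) |
| Direct bilirubin | yes | excluded | no | no |

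Five measures are excluded, three have a categorical replacement, and 5 − 3 = 2 have none. SAP Table 6.2 sets population and baseline rules for categorical chemistry analyses as a group. It does not reverse the exclusion.

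**Step 2. Each protocol ALP criterion against the SAP outputs.**

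| Criterion | Source | Tabulated | Always listed |
|---|---|---|---|
| ALP ≥2X ULN | Protocol 9.4.6 | no | no |
| ALP >3X ULN | Protocol 8.1.1 | no | no |
| ALP >2.5X with total bilirubin >2X ULN | Protocol 8.1.1 | no | yes, because bilirubin >2X meets the ≥2X trigger |
| ALP >2.5X ULN with symptoms or eosinophilia | Protocol 8.1.1 | no | no |

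So 0 of 4 criteria are tabulated and 1 of 4 always reaches the listing. The other three reach it only if ALT, AST or total bilirubin is also raised.

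**Step 3. What the continuous analysis can show.** Table 6.2 restricts the continuous laboratory analyses to planned tests, and the SAP revision history says that unplanned tests were removed from the last-observation analysis. Repeat ALP values from the monitoring in Protocol 9.4.6 therefore enter no comparison of arms. The ANCOVA compares means, which a few high values barely move. As an illustration, with 670/2 = 335 patients per arm and an assumed k patients rising by an assumed 2X ULN, the shift is k × 2/335:

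- k = 1: 0.006X ULN
- k = 2: 0.012X ULN
- k = 5: 0.030X ULN

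The descriptive summary does include the arm maximum (SAP 6.1). It is reported in SI and conventional units. It shows that one value was high, but not how many patients crossed a multiple of ULN.

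**Step 4. Baseline.** Protocol 6.2 sets screening limits for total bilirubin, ALT and AST but none for ALP. Patients may enter with raised ALP, and the treatment-emergent high table takes only patients with a normal baseline. This is why an ALP row by baseline category is needed as well as a return to the 6.12.5 tables.

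**The case against.** The strongest reply is that ALP is far from unanalysed and little is lost.

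- Continuous summaries include the maximum by arm, so an extreme planned value would be visible.
- Chemistry is scheduled only at Visits 1, 8 and 18 and at early discontinuation. The Week 26 and last-value analyses therefore use nearly all planned post-baseline ALP results, and a table of rises at any time would mainly add unplanned tests.
- ALP is shown for every patient flagged by ALT, AST or total bilirubin.
- SAP 6.12.4.4.1 searches adverse events for liver investigations and cholestasis terms, 6.12.2 tabulates and lists adverse events leading to IP discontinuation, and 6.12.8 adds narratives.
- The SAP does not set out to mirror the protocol's action thresholds: its ALT and AST rows are 3X, 5X and 10X, while 8.1.1 uses 3X, 5X and 8X.

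All of this is correct and limits the point. A reader might infer that a cholestatic patient would appear in no table, profile or listing. The documents do not support that, given the arm maxima, the adverse-event route and the bilirubin-triggered listing. Nor do they support a count of patients missed: they give no ALP incidence, and any such count would also have to assume that every rise is isolated. The ALP criteria in 8.1.1 do not mandate stopping either. They are conditions to be considered after consultation with the medical monitor.

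What the reply does not supply is a count. The adverse-event route depends on reporting, and Protocol 9.4.5 requires a laboratory finding to be reported as an adverse event only when it is clinically significant and results in a diagnosis. Unplanned tests matter because hepatic follow-up generates them.

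A side issue is AST. Protocol 8.1.1 acts on either transaminase, for example "ALT or AST >5X ULN for more than 2 weeks", while the 9.4.6 monitoring trigger does not name AST. One might infer that a patient with AST alone raised is not followed. That goes too far: Protocol 9.2 requires documented review of every laboratory safety report, and Appendix 4 covers any treatment-emergent hepatic abnormality and includes AST. It is a wording mismatch.

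**Conclusion.** The point holds as a gap in safety reporting. Two of the five liver measures, ALP and direct bilirubin, have no categorical laboratory analysis, because the exclusion in SAP 6.12.5 relies on a replacement that 6.12.4.4.3 does not provide for them. An isolated ALP rise, including one at the protocol's 2X ULN monitoring trigger or its 3X ULN criterion for considering IP discontinuation, is counted in no laboratory-threshold output.

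The conclusion rests on reading the liver measures in 6.12.5 as defined in 6.12.4.4.2. A narrower reading, that bilirubin is not an enzyme, would return direct bilirubin to the tables but still leave ALP out. The protocol sets no threshold for direct bilirubin, so the mismatch with protocol criteria concerns ALP alone. The number of patients affected cannot be derived from the documents. The primary and multiplicity-adjusted analyses are not touched.

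**What to change.** 1. In SAP 6.12.5, limit the exclusion from the treatment-emergent abnormal, high and low tables to ALT, AST and total bilirubin, so that ALP and direct bilirubin return to them. The continuous analyses of all five measures can stay in 6.12.4.4.2.
2. In SAP 6.12.4.4.3, add an ALP elevation row by baseline category, planned and unplanned tests included, at thresholds the protocol already uses, for example ≥2X and >3X ULN.
3. Add ALP ≥2X ULN to the trigger for the profiles and listing. Values above 2.5X and 3X also satisfy ≥2X, so patients meeting any of the four protocol ALP criteria would then be listed (4 of 4, against 1 of 4 assured now).
4. Separately, reconcile the wording of Protocol 9.4.6 and 8.1.1 on AST. Which wording is right is a clinical matter for the sponsor.

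Items 1 to 3 cost a few lines of SAP text and a few table rows from data already in the database. SAP 6.1 allows analysis changes that do not alter a principal feature of the protocol to be recorded in the SAP or the clinical study report, so these items need no protocol amendment. Item 4 is a one-line clarification.
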